1.4 Study Design

This is a prospective, single-arm, multicenter, phase-IV trial investigating the safety of osimertinib in Indian adult patients with metastatic EGFR-T790M mutation-positive NSCLC. Investigator will be trained on the locally approved prescribing information before the enrolment of the first patient at their site to ensure compliant and proper dosing of the study drug. Patients will be monitored throughout the study period for AEs of osimertinib.

2. Study Objectives

Primary Objective:	Primary Outcome Measure:
To assess the safety of osimertinib among T790M positive NSCLC patients of India	• Number, frequency and proportion of patients with adverse events (AEs), serious adverse events (SAEs) and AEs of special interest (AESI) including interstitial lung disease/pneumonitis-like events, and on-study deaths.

3. Patient Selection, Enrolment, Randomisation, Restrictions, Discontinuation and Withdrawal

Each patient should meet all of the inclusion criteria and none of the exclusion criteria for this study. Under no circumstances can there be exceptions to this rule.

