The Treatment Phase will extend from Cycle 1, Day 1 to Cycle 6, Day 21; or until study drug discontinuation due to either disease progression or unacceptable toxicity; or other reasons whichever occurs first, as listed in Section 3.9. Details of the procedures performed during the Treatment Phase are outlined in the Time and Events Schedules. Patients will be closely monitored for adverse events and other safety evaluations including laboratory investigations, concomitant medications. If disease progression is diagnosed before Cycle 6, Day 21, then the patient will discontinue study drug with completion of the End-of-Treatment Visits on the day of progression, and will enter the Follow-up Phase.

END-OF-TREATMENT VISIT (EOT)

An End-of-Treatment Visit is to be scheduled on Cycle 6, Day 21 of the study drug administration. In a case where patient discontinues the study treatment for any reason listed in Section 3.9 before Cycle 6, Day 21, last visit of the patient will be considered as End-of-treatment visit. Every effort should be made to conduct the telephonic End-of-Study Visit before the patient starts subsequent treatment.

FOLLOW UP PHASE (END-OF-STUDY)

A telephonic follow-up will be conducted 28 days after the EOT Visit. This will be considered as End-of-study visit.

The observation period including the Enrolment Visit and telephonic end-of-study visit will be up to a maximum duration of approximately 23 weeks for each patient.

5. Study Assessments

The investigator ensures the accuracy, completeness, and timeliness of the data recorded and of the provision of answers to data queries according to the Clinical Study Agreement.

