8.5.1 Analysis of the primary variable (s)

Adverse Events

The verbatim terms used in the CRF by investigators to identify adverse events will be coded using the Medical Dictionary for Regulatory Activities (MedDRA) and CTCAE grade and will be listed individually by patient. Treatment-emergent adverse events are adverse events with onset during the treatment phase or that are a consequence of a pre-existing condition that has worsened since baseline. All reported adverse events will be included in the analysis. For each adverse event, the percentage of subjects who experience at least 1 occurrence of the given event will be summarized.

Any AE occurring before treatment with osimertinib will be included in the data listings but will not be included in the summary tables of AEs. Any AE occurring within 28 days of discontinuation of investigational product (ie, the last dose of osimertinib) will be included in the AE summaries.

Any events in this period that occur after a patient has received further therapy for cancer (following discontinuation of osimertinib) will be flagged in the data listings.

Adverse events of special interest (for example interstitial lung disease/pneumonitis-like events; QTc prolongation events]) will be summarized separately.

Summaries, listings, datasets, or subject narratives may be provided, as appropriate, for those subjects who die, who discontinue treatment due to an adverse event, or who experience a severe or a serious adverse event.

Clinical Laboratory Tests

Laboratory data will be summarized by type of laboratory test. Descriptive statistics will be calculated for each laboratory analyte at baseline and for observed values and changes from baseline at each scheduled time point. Changes from baseline results will be presented in pre- versus posttreatment cross-tabulations (with classes for below, within, and above normal ranges). Parameters with predefined National Cancer Institute Common Terminology Criteria for Adverse Events (NCI-CTCAE) toxicity grades will be summarized. Change from baseline to the worst adverse event grade experienced by the subject during the study will be provided as shift tables. A listing of subjects with any laboratory results outside the reference ranges will be provided. A listing of subjects with any markedly abnormal laboratory results will also be provided.

Electrocardiogram (ECG)

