### Schematic Overview of the Study

## 4. Sample Size and Power Considerations

*The primary objective of the trial is to describe the safety profile of osimertinib in routine clinical practice and add to the limited burden of safety data on osimertinib currently available as assessed by the incidence of adverse events*

(AEs) (Serious and Non-serious AEs) observed during trial. Considering the epidemiology of metastatic NSCLC-adenocarcinoma subtype which are positive for EGFR sensitizing mutation and have progressed after EGFR-TKI based treatment in first line setting and prevalence of T790M-mutation after such progression, a sample size of 60 patients is expected to provide the following exact two sided 95% confidence interval for a list of percentages of patients reporting at least one AE (Julious and Campbell 2012).

Observed rate expressed as % (number of patients reporting at least one AE*)	Lower Limit of CI (%)	Upper Limit of CI (%)
0%	0	6.0
1%	0	7.8
2%	0.1	9.5
5%	1.0	13.9
10%	3.8	20.5
20%	10.8	32.3
30%	18.8	43.2
40%	27.6	53.5
50%	36.8	63.2

\*the symptom could be any of the expected AE, unexpected AE or SAE. The calculation is based on the link between binomial and beta distributions.

In order to enroll approximately 60 patients, it is expected that approximately 70 patients will be screened.

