## 7. Method of Analysis

### 7.1 Statistical Hypotheses

*No formal hypothesis testing will be conducted.*

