## 8.7 Safety Analysis

### 8.7.1 Adverse Events

All adverse events (AEs) will be coded by System Organ Class (SOC) and Preferred Term (PT) according to the Medical Dictionary for Regulatory Activities (MedDRA) Version 23.0. The intensity of adverse events is graded by the National Cancer Institute (NCI) Common Terminology Criteria for Adverse Events (CTCAE) version 4.0 or higher.

*Treatment-emergent adverse events are adverse events with onset during the treatment phase or that are a consequence of a pre-existing condition that has worsened since baseline. All reported adverse events will be*

*included in the analysis. For each adverse event, the percentage of subjects who experience at least 1 occurrence of the given event will be summarized.*

*Any AE occurring before treatment with osimertinib will be included in the data listings but will not be included in the summary tables of AEs. Any AE occurring within 28 days of discontinuation of investigational product (i.e., the last dose of osimertinib) will be included in the AE summaries.*

*Any events in this period that occur after a patient has received further therapy for cancer (following discontinuation of osimertinib) will be flagged in the data listings.*

*Adverse events of special interest (for example interstitial lung disease/pneumonitis-like events; QTc prolongation events) will be summarized separately.*

*Summaries, listings, datasets, or subject narratives may be provided, as appropriate, for those subjects who die, who discontinue treatment due to an adverse event, or who experience a severe or a serious adverse event.*

An overall summary will be provided in terms of count and percentages for:

- AEs
- TEAEs
- Grade 3 and above TEAEs
- Grade 3 and above related TEAEs
- Treatment-related TEAEs
- Treatment-related serious TEAEs
- TEAEs leading to dose change/ interruption/ discontinuation
- Treatment related TEAEs leading to dose change/ interruption/ discontinuation
- Serious TEAEs
- Fatal TEAEs
- Related Fatal TEAEs

Summaries in terms of count and percentages by SOC and PT will be provided for the following:

- TEAEs
- Treatment-Emergent SAEs
- Grade 3 and above TEAEs
- Treatment-related TEAEs
- Grade 3 and above treatment-related TEAEs
- TEAEs leading to dose change/ interruption/ discontinuation
- Adverse Events of special interest

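### All-cause AE summaries can include toxicity of the next cancer therapy, and no planned table shows the figures with and without those events

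*SAP*

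**What the plan says.** The inclusion rule is the same in both documents. SAP 8.7.1: "Any AE occurring within 28 days of discontinuation of investigational product (i.e., the last dose of osimertinib) will be included in the AE summaries". Protocol 8.5.1 has the same sentence. For events in that window with onset after a switch, SAP 8.7.1 says "Any events in this period that occur after a patient has received further therapy for cancer (following discontinuation of osimertinib) will be flagged", and it places that flag in the listings. Neither document removes them from a summary, cuts the window at the start of new therapy, or plans a table without them.

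Other provisions that bear on the point:

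- **Objective** (Protocol section 2): "To assess the safety of osimertinib among T790M positive NSCLC patients of India". The outcome measure is the number and proportion of patients with AEs, SAEs, AEs of special interest (AESIs) and on-study deaths. It has no causality restriction.
- **When osimertinib stops** (Protocol section 4; SAP 5.2): a patient who progresses before Cycle 6 Day 21 stops the drug, has the End-of-Treatment visit on the day of progression and enters follow-up.
- **Timing of the last call** (Protocol section 4): the telephone visit is set 28 days after End of Treatment, but "Every effort should be made to conduct the telephonic End-of-Study Visit before the patient starts subsequent treatment".
- **TEAE, first rule** (SAP 8.7.1): onset in the treatment phase, or worsening of a pre-existing condition.
- **TEAE, second rule** (end of SAP 7.3): an AE that did not end before the first dose is a TEAE. No upper time limit is given.

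**The concern.** Osimertinib stops on the day progression is found, so the next line of treatment can begin well inside the 28 days. Toxicity that starts after that switch enters the all-cause figures for osimertinib. There is no control arm against which to judge the excess, and the tables themselves do not show how many patients are counted only because of such an event.

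The effect is greatest for uncommon terms. With 60 patients, each extra patient moves a percentage by 1.7 points (1/60), and one or two can change how a rare event reads.

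**Working it through.** **1. Which tables are exposed.** Take a new AE, not a worsening of an existing condition, that starts after the switch and within 28 days of the last dose.

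| Rule | Where | Result for this AE |
|---|---|---|
| 28-day sentence | SAP 8.7.1, Protocol 8.5.1 | In the AE summaries |
| TEAE by onset in the treatment phase | SAP 8.7.1; SAP 5.2 ends that phase at discontinuation | Not a TEAE |
| TEAE unless ended before first dose | End of SAP 7.3 | TEAE |

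The planned outputs in SAP 8.7.1 then divide as follows:

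- The overall AEs row carries the event on any reading.
- The AESI table by system organ class and preferred term is not labelled as TEAE-only, so it may carry it.
- All other rows and tables are TEAE outputs. They carry it only if SAP 7.3 or the 28-day sentence overrides the definition.
- The treatment-related outputs also need a positive investigator causality rating (Protocol 6.3.4).

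**2. The plan's own figures.** SAP section 4 says "a sample size of 60 patients is expected to provide the following exact two sided 95% confidence interval", and SAP 7.1 says "No formal hypothesis testing will be conducted". There is no power figure to check, only the interval table. Exact limits are lower = Beta(0.025; x, n-x+1) and upper = Beta(0.975; x+1, n-x), with n = 60 and x = 60 × rate. For 0% they give 0 to 5.96 (stated 0 to 6.0). For 5% they give 1.04 to 13.92 (stated 1.0 to 13.9). For 10% they give 3.76 to 20.51 (stated 3.8 to 20.5). All nine rows agree to within 0.1 point.

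**3. How many patients could switch.** Inputs: median PFS on osimertinib of 10.1 months in the cited phase III trial (Protocol 1.1), and a treatment phase of 6 × 21 = 126 days, or 126/30.4375 = 4.14 months. An exponential course is assumed.

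- Share progressing = 1 - exp(-ln 2 × 4.14/10.1) = 0.247, and 0.247 × 60 = 14.8 patients.
- A median of 8 months gives 18.1 patients; a median of 12 months gives 12.8.

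**4. Patients added to one AE term.** The documents give neither the share switching within 28 days nor the AE rate on the next therapy. Both are assumed here, at 25-75% and 10-50%. Added patients = 60 × share discontinuing × share switching × AE rate.

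| Discontinuing | Switching | AE rate | Patients added | Points |
|---|---|---|---|---|
| 25% | 25% | 10% | 0.4 | 0.6 |
| 25% | 50% | 30% | 2.3 | 3.8 |
| 25% | 75% | 50% | 5.6 | 9.4 |

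Letting discontinuation run from 15% to 35% widens the range to 0.2 to 7.9 patients.

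**5. Effect on a reported rate (exact 95% intervals, n = 60).**

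| Without post-switch events | Patients added | With them |
|---|---|---|
| 0/60: 0% (0 to 6.0) | 1 | 1.7% (0.0 to 8.9) |
| 0/60: 0% (0 to 6.0) | 3 | 5.0% (1.0 to 13.9) |
| 3/60: 5.0% (1.0 to 13.9) | 2 | 8.3% (2.8 to 18.4) |
| 6/60: 10.0% (3.8 to 20.5) | 3 | 15.0% (7.1 to 26.6) |

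**The case against.** Including and flagging is a prespecified and conservative safety rule. A cut at the next therapy could take a delayed osimertinib event, such as interstitial lung disease, out of the main tables. This stands, and it is why the 28-day count should remain the main presentation.

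A reader might go further and infer that the next drug's toxicity is reported as osimertinib's throughout the term-level tables. The documents do not support that. Under the SAP 8.7.1 definition a new follow-up event is not a TEAE, and every table by preferred term except the AESI table is a TEAE table. SAP 7.3 points the other way, but its sentence closes a section on missing dates, so its reach is arguable. Causality is rated for every event, and the treatment-related tables give partial separation. They do not correct the all-cause figures, and no related-only AESI table is planned.

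Nor are the events hidden altogether. With about 60 patients, anyone holding the flagged listings can count them. A reader of the tables alone cannot.

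The arithmetic in step 4 also leans high, for reasons in the documents:

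- A patient counts once per term, so one who already had that term on osimertinib adds nothing.
- The open AE question runs only to the last telephone contact (Protocol 6.3.5). If the call precedes the switch, later events are not solicited.
- No laboratory tests are scheduled after End of Treatment (Protocol Table 1). Deterioration in a mandated test is an AE only if it is serious or the reason for stopping study drug (Protocol 6.3.6), which limits symptom-free laboratory toxicity.
- Some PFS events are deaths, and a switcher contributes only what is left of the 28 days.

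**Conclusion.** The point holds in a limited form. The all-cause summaries can include AEs of the next therapy, and no planned table shows or removes them. The overall AEs row is certainly open to this and the AESI table possibly. The TEAE tables depend on a conflict between SAP 7.3 and SAP 8.7.1 that the plan leaves open.

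The size cannot be fixed from the documents. The range of 0.4 to 5.6 patients per term rests on an exponential course, progression as the only route off treatment, and assumed switching and AE rates. It makes no allowance for the limits listed under the objection. A narrow estimate of the inflation would not be justified. This is an inexpensive improvement to reporting, not a flaw that invalidates the primary analysis.

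**What to change.** In SAP 8.7.1:

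1. State one TEAE window and reconcile it with the last paragraph of SAP 7.3 and with the 28-day sentence.
2. Keep the 28-day all-events summary as the main presentation.
3. Add rows for AEs, SAEs, grade 3 or higher AEs and AESIs that exclude events with onset on or after the start of further anticancer therapy.
4. Tabulate the flagged events separately.
5. Name the CRF start date of subsequent therapy that drives the flag. SAP 8.4 has categories only for prior medication and medication taken while on study drug, and SAP 8.7.5 lists only previous cancer therapy. Therapy first started after the last dose has no stated place, although Protocol Table 1 records concomitant medication to 28 days after the last dose.

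The cost is SAP wording and a few table rows, with no new visits. If step 1 departs from the TEAE definition in Protocol 8.5.1, the sponsor must decide whether that is a substantial change under Protocol 10.5. A delayed osimertinib event after a switch would be absent from the excluding rows, but it stays in the main summary.

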#### 8.7.2 Clinical Laboratory Tests

*Laboratory data will be summarized by type of laboratory test. Descriptive statistics (N, Mean, SD, Median, Minimum and Maximum) will be calculated for each laboratory analyte at baseline and for observed values and changes from baseline at each cycle.*

The baseline measurement is the last predose measurement taken before Cycle1 Day1.

**Haematology/Haemostasis (whole blood)**

Haemoglobin (Hb)

Leukocyte count

**Clinical Chemistry (serum or plasma)**

Creatinine

Bilirubin, total

Leukocyte differential count (absolute count)	Alkaline phosphatase (ALP)
Platelet count	Aspartate transaminase (AST)
	Alanine transaminase (ALT)
	Albumin
	Potassium
	Calcium, total
	Sodium
	Creatine kinase (CK)

*Changes from baseline results will be presented in pre- versus post treatment cross-tabulations (with classes for below, within, and above normal ranges). Parameters with predefined National Cancer Institute Common Terminology Criteria for Adverse Events (NCI-CTCAE) toxicity grades will be summarized. Change from baseline to the worst adverse event grade experienced by the subject during the study will be provided as shift tables.*

Lab toxicity grades will be derived using NCI-CTCAE version 5.0.

*A listing of subjects with any laboratory results outside the reference ranges will be provided. A listing of subjects with any markedly abnormal laboratory results will also be provided.*

*Physical Examinations*

*A listing of physical examinations will be provided.*

**8.7.3 Vital Signs**

Descriptive statistics (N, Mean, SD, Median, Minimum and Maximum) will be provided for vital signs parameters (pulse rate, Systolic blood pressure, Diastolic blood pressure, weight) for the observed values and change from baseline at each cycle. The corresponding listing will be provided.

The baseline measurement is the last predose measurement taken before Cycle1 Day1.

**8.7.4 Electrocardiogram**

QTc Interval data will be descriptively summarized. Descriptive statistics (N, Mean, SD, Median, Minimum and Maximum) will be calculated at baseline and for observed values and changes from baseline at each scheduled time point. *The ECG will be evaluated by the investigator and entered as “Normal” or “Abnormal” in the eCRF. If the ECG is evaluated as “Abnormal” the abnormality is further specified. Frequency tabulations of the abnormalities will be made.*

The baseline measurement is the last predose measurement taken before Cycle1 Day1.

The number (%) of participants with maximum post-dose QTc values and maximum increases from baseline in the following categories will be tabulated for each cycle.

Safety QTc interval

QTc interval			
Absolute value	≥450 <480	>=480-<500 ≥480	>=500
Absolute change	30- <60	≥60	

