Visit No.	1	2-7 (Day 1 of each cycle)	8	202
Study Days	-6 to 0	1-109 (21 day per cycle)	131	28 days post- EOT
Screening/Enrolment visit				
Informed consent ^(b)	Patients r	nust sign the informed conser procedures are p		study-specific
Eligibility Criteria	X			
Demographics/ Review medical history	X			
WHO Performance Status	X	X	X	
General Physical examination	X	Symptom-directed physical	examination only	
Concomitant medication recording	Continuous from time of ICF until 28 days after last osimertinib dose in treatment phase.			
Study Drug Administration				
Osimertinib dosing		The recommended dose is 80 mg osimertinib once a day until disease progression or unacceptable toxicity. Each cycle is of 21 days.		
Disease Evaluations (Disease char	racteristics wil	ll be performed as per routine	clinical practice)	
Baseline Disease Characteristics	X			
Safety Evaluations				
Physical examination	X	Symptom-directed physical examination only		
Vital parameters	X	X	X	
Adverse event monitoring		us from time of ICF until 28 days after last study osimertinib dose		
12-lead ECG	X	X	X	
Hematology & Biochemistry	X	X	X	

Footnotes:

- a. The Screening Phase begins when the first Screening procedure is conducted. Screening tests should be performed within 7 days of Cycle 1 Day 1 except for disease evaluations (performed as routine clinical practice).
- b. Must be signed before first study-related activity.

TABLE OF CONTENTS

PAGE

TITLE	PAGE	1
VERSIO	ON HISTORY	2
PROTO	COL SYNOPSIS	3
TIME A	AND EVENTS SCHEDULE	8
TABLE	OF CONTENTS	9
1.	Introduction	13
1.1	Background and rationale for conducting this study	13
1.2	Rationale for study design, doses and control groups	14
1.3	Benefit/risk and ethical assessment	14
1.4	Study Design	14
2.	Study Objectives	14
3.	Patient Selection, Enrolment, Randomisation, Restrictions, Discontinuation and Withdrawal	15
3.1	Inclusion criteria	15
3.2	Exclusion criteria	15
3.3	Patient enrolment and randomization	15
3.4	Procedures for handling incorrectly enrolled or patients	16
3.5	Methods for assigning treatment groups	16
3.6	Methods for ensuring blinding	16
3.7	Methods for unblinding	16
3.8	Restrictions	16
3.9 3.9.1	Discontinuation from study treatment Procedures for discontinuation of a patient from study drug	
3.10 3.10.1	Criteria for withdrawal	
3.11	Discontinuation of the study	18
4.	Study Plan and Timing of Procedures	19
5.	Study Assessments	20
5.1 5.1.1 5.1.2 5.1.3	Safety assessments Laboratory safety assessments Physical examination	21

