If new or worsening pulmonary symptoms (e.g., dyspnoea) or radiological abnormality suggestive of interstitial lung disease is observed, an interruption in study treatment dosing is recommended, and the AstraZeneca study team should be informed. It is strongly recommended to perform a full diagnostic workup, to exclude alternative causes such as lymphangitic carcinomatosis, infection, allergy, cardiogenic edema, or pulmonary hemorrhage. The results of the full diagnostic workup (including high-resolution computed tomography, blood and sputum culture, haematological parameters) will be recorded in the CRF by the investigator. In the presence of confirmatory HRCT scans where other causes of respiratory symptoms have been excluded, a diagnosis of interstitial lung disease (ILD) should be considered and study treatment permanently discontinued.

In the absence of a diagnosis of ILD study treatment may be restarted following consultation with the AstraZeneca Study Team Physician.

QTc prolongation

Patients with QTcF prolongation to >500 msec should have study treatment interrupted and regular ECGs performed until resolution to <481 msec or recovery to baseline if baseline QTcF is >481 msec and then restarted at a reduced dose of 40 mg. If the toxicity does not resolve to ≤grade 1 within 21 days the patient will be permanently withdrawn from study treatment.

Keratitis

Patients presenting with signs and symptoms suggestive of keratitis such as acute or worsening: eye inflammation, lacrimation, light sensitivity, blurred vision, eye pain and/or red eye should be referred promptly to an ophthalmology specialist.

Changes in cardiac contractility

In patients with cardiac risk factors and those with conditions that can affect LVEF, cardiac monitoring, including an assessment of LVEF at baseline and during treatment, should be considered. In patients who develop relevant cardiac signs/symptoms during treatment, cardiac monitoring including LVEF assessment should be considered.

Patients experiencing corneal ulceration, Interstitial Lung Disease (ILD) or QTc prolongation with signs/symptoms of serious arrythmia will not be permitted to restart study treatment.

For the details, please refer to the local prescribing information.

7. Study Drug and Other Treatments

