8.3 Description of outcome variables in relation to objectives

Analysis will be conducted to evaluate the following as available in the CRF:

- Baseline characteristics: demographics, relevant medical history, disease characteristics, cancer treatment history.
- Exposure to the study drug
- Adverse events SAEs, AEs leading to dose modification or discontinuation, and AEs of special interest (for example interstitial lung disease/pneumonitis-like events; QTc prolongation events)
- Death due to AE, or unknown cause (except death due to disease progression).

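### SAP 8.7.4 counts QTc outliers cycle by cycle only, so no output named in the plan gives the number of patients who ever crossed a QTc threshold

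*SAP*

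**What the plan says.** QTc prolongation is one of the examples of an adverse event of special interest: protocol 8.3 lists "QTc prolongation events" beside interstitial lung disease, and protocol 8.5.1 and SAP 8.7.1 do the same. The primary outcome (protocol section 2) is the number, frequency and proportion of patients with adverse events, serious adverse events and events of special interest.

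For measured QTc, SAP 8.7.4 plans three things:

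- descriptive statistics, including the maximum, at each scheduled time point;
- frequencies of the abnormalities that investigators specify;
- a category table, in which patients with "maximum post-dose QTc values and maximum increases from baseline in the following categories will be tabulated for each cycle".

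The absolute bands start at 450, 480 and 500 msec, and the change bands at 30 and 60 msec. The middle absolute cell reads ">=480-<500 ≥480" in the extracted text. That may be a conversion fault, and nothing below depends on it.

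Table 1 of the protocol places the treatment-phase ECGs at visits "2-7 (Day 1 of each cycle") and at a separate EOT visit.

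On action thresholds, the QTc paragraph of protocol 6.7 says "Patients with QTcF prolongation to >500 msec should have study treatment interrupted". Table 3 in the same section sets its rule on QTc above 500 msec on two or more separate ECGs.

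**The concern.** A safety report on a drug with a QTc signal is normally expected to say how many patients ever had a QTc at or above a given value, or ever rose by a given amount. Cycle-by-cycle counts do not answer that. One patient shown in each of three cycles may be one person or three, and the denominator falls as patients stop. With one scheduled ECG per cycle, the maximum within a cycle is usually just that single reading.

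At stake is the measured evidence on an event of special interest. Protocol 6.3.6 keeps most worsening in mandated assessments out of the adverse-event data on the ground that those results are summarised in the study report. If the summary is only per cycle, an asymptomatic, non-serious QTc prolongation may never be counted per patient anywhere.

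**Working it through.** 1. **The plan's own figure.** SAP section 4 says "a sample size of 60 patients is expected to provide the following exact two sided 95% confidence interval" and "The calculation is based on the link between binomial and beta distributions". That is the Clopper-Pearson interval: lower limit = Beta(0.025; x, n−x+1), upper limit = Beta(0.975; x+1, n−x), with n = 60. All nine rows reproduce to one decimal. For example, x = 6 (10%) gives 3.76 to 20.51 against the stated 3.8 to 20.5. The table is sound, and the same formula is used below.

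2. **Number of post-dose ECGs per patient.** Day 1 of Cycles 2 to 6 gives five, and EOT makes six. SAP 8.7.4 defines baseline as the last predose value before Cycle 1 Day 1 and does not say whether the Cycle 1 Day 1 tracing counts as post-dose. If it does, there are seven.

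3. **What the separate counts determine.** Let c₁ … c_K be the numbers of patients in the top category at K visits. The number who were ever in it, N, satisfies max(c) ≤ N ≤ min(60, Σc). The lower end is the same patients each time, and the upper end is different patients each time. If crossings were independent across visits, the expected proportion would be 1 − (1 − c/60)^K.

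4. **Illustration.** The documents give no QTc rate, so c is assumed, and all 60 patients are taken to have every ECG.

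| Patients per visit | K | Fewest ever (95% CI, %) | Most ever (95% CI, %) | If independent |
|---|---|---|---|---|
| 1 (1.7%) | 6 | 1/60 = 1.7% (0.0–8.9) | 6/60 = 10.0% (3.8–20.5) | 9.6% |
| 1 (1.7%) | 7 | 1/60 = 1.7% (0.0–8.9) | 7/60 = 11.7% (4.8–22.6) | 11.1% |
| 2 (3.3%) | 6 | 2/60 = 3.3% (0.4–11.5) | 12/60 = 20.0% (10.8–32.3) | 18.4% |
| 2 (3.3%) | 7 | 2/60 = 3.3% (0.4–11.5) | 14/60 = 23.3% (13.4–36.0) | 21.1% |

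5. **Do other named outputs supply N?**
   - *Special-interest and adverse-event tables (SAP 8.7.1).* These count reported events. Protocol 6.3.6 limits reporting of worsening in mandated assessments to cases that are serious or cause discontinuation of study drug. Accompanying signs or symptoms are reported in their own right, with the finding as supporting information. Table 3 describes withholding and restarting for its QTc criterion, so an asymptomatic, non-serious case handled that way need not be an adverse event. It would then also be absent from the table of events leading to dose change or interruption.
   - *Abnormality frequencies (SAP 8.7.4).* These follow the investigator's description and are not tied to a QTc value.
   - *Maximum at each time point (SAP 8.7.4).* This shows whether anyone crossed at a visit, not how many different people did over the study.
   - *Listings.* SAP 8.7.4 names no ECG listing and ECG is not on the 8.7.5 list, whereas vital signs get a listing in 8.7.3.
   - *Contrast.* For laboratory data, SAP 8.7.2 already plans shifts to the worst grade over the study.

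6. **Thresholds side by side.** The SAP's top band is 500 msec or more on any reading. Table 3 uses more than 500 msec on at least two separate ECGs. The protocol 6.7 text uses QTcF above 500 msec without the two-ECG condition. The SAP does not name its QT correction.

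**The case against.** The strongest reply is that this is a 60-patient, single-arm, descriptive study (SAP 7.1: "No formal hypothesis testing will be conducted"), so no inference is biased, and the any-time count can be derived from the collected data whenever it is wanted. The word maximum suggests that a worst-on-treatment table may have been intended, and the table shells are not in the documents. The primary outcome counts reported events and names only lung events outright; QTc enters as an example, so the category table is supportive. The planned outputs are also not empty: if every visit maximum lies below a threshold, nobody with a recorded visit value crossed it, and otherwise the counts bound the answer as in step 3.

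Most of this stands, and it limits the weight of the point. It does not remove it. Followed as written, the SAP yields cycle counts only, and an any-time count added after the data are seen would be a post hoc choice.

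A reader might also infer that the EOT ECG is left out of the table. The documents do not show that. The protocol and SAP 5.2 place EOT on Cycle 6 Day 21, which is 6 × 21 = Day 126, so it may be counted within Cycle 6. Table 1 gives EOT its own column and Day 131. Its place is unstated, not excluded. If it is pooled with Cycle 6 and Cycle 1 Day 1 is not post-dose, there are five rows, and one patient per row fits 1/60 (1.7%) to 5/60 (8.3%).

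**Conclusion.** The point holds as a gap in the named outputs. SAP 8.7.4 gives cycle counts that bound the number of patients who ever crossed a QTc threshold without fixing it, and the adverse-event summaries do not replace that number because of protocol 6.3.6. In the illustration, one patient per visit fits 1.7% to 10.0% with six post-dose ECGs. This rests on an assumed count, complete attendance at all visits, and no any-time row in table shells that the documents do not include.

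Two stronger readings are tempting, and the documents do not support them:

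- *That the plan understates QTc incidence about six-fold.* The understatement is nil if the same patients cross each time. It nears six-fold only if crossings are independent or fall on different patients, and nothing in the documents supports either.
- *That the SAP bands are wrong because they differ from the protocol's action threshold.* The difference between at least 500 and above 500 matters only for a reading of exactly 500 msec. Likewise, the SAP's 480 boundary and the protocol's recovery value of below 481 part only at 480 msec. The two-ECG condition in Table 3 is the larger difference, and re-cutting single-reading bands would not capture it. Nor does any passage require descriptive bands to equal a dosing rule. What remains is that the SAP band, Table 3 and the 6.7 text differ and must be reconciled; no view is taken here on which rule is right.

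**What to change.** In SAP 8.7.4:

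- For both the absolute and the change categories, add a row for any time after first dose. Count each patient once, at the worst value over all scheduled and unscheduled post-dose ECGs, including EOT.
- Use as denominator the patients with at least one post-dose ECG and, for the change categories, also a baseline ECG.
- Keep the per-cycle rows. State whether EOT is counted in Cycle 6 or shown separately, and whether the Cycle 1 Day 1 ECG is post-dose.
- Name the QT correction that is tabulated.

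Separately, the sponsor should reconcile the 500 msec wording across SAP 8.7.4, protocol Table 3 and the QTc paragraph of protocol 6.7. The SAP bands need not be re-cut for this point.

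The cost of the SAP change is a few sentences and a few added rows in one table. It needs no new data or visits.
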